#### **6.6.4 Use of SZC/Placebo for Management of Serum Potassium Immediately after Randomised Withdrawal (Up to Week 6 of Maintenance Phase)**

At Visit 6b, the participant is randomised to SZC or placebo (ie, to withdraw SZC and receive placebo), at the same dose as the last dose of SZC during the run-in phase. Lisinopril/valsartan is continued at the same dose received at the end of the run-in phase. As the investigator and the participant are blinded to the SZC/placebo treatment assignment, specific instructions for management of S-K during the period immediately following randomisation are provided below. All participants must return for Visit 7 exactly 2 days after randomisation.

**Note:** Use **Table 8** for STEP-wise dose adjustments and Section **6.5.2** for information about rescue therapy.

##### **Visit 7 (2 days after Visit 6b/randomisation)**

- If S-K  $\geq 3.5$  and  $\leq 5.0$  mmol/L, continue lisinopril/valsartan at the same dose; the participant must return 5 ( $\pm 1$ ) days later to Visit 8 for a local S-K laboratory measurement.
- If S-K is  $> 5.0$  and  $\leq 5.5$  mmol/L and SZC/placebo IS NOT at maximum of 15 g QD, increase SZC/placebo to 15 g QD AND reduce lisinopril/valsartan one step. If lisinopril/valsartan is at the lowest dose, pause dosing and assess re-initiation of these agents at starting doses (STEP 1) during the next visit. The participant must return 5 ( $\pm 1$ ) days later to Visit 8 for a local S-K laboratory measurement.
- If S-K is  $> 5.0$  and  $\leq 5.5$  mmol/L and SZC/placebo IS at maximum of 15 g QD, reduce lisinopril/valsartan one step. If lisinopril/valsartan is at the lowest dose (STEP 1), pause dosing and assess re-initiation of these agents at STEP 1 starting doses during the next visit. The participant must return 5 ( $\pm 1$ ) days later to Visit 8 for a local S-K laboratory measurement.
- If S-K is  $> 5.5$  mmol/L and:
  - Lisinopril/valsartan is at the lowest dose, permanently discontinue lisinopril/valsartan and consider short-term rescue therapy and management of hyperkalaemia as per SoC at the investigator's discretion and local practice. Follow up at Visit 8 for monitoring of local S-K laboratory value.
  - Lisinopril/valsartan is at mid-range (STEP 2) or maximum dose (STEP 3), pause lisinopril/valsartan and SZC/placebo, and give short-term rescue therapy as per SoC at the investigator's discretion (24 to 48 hours rescue treatment); re-start SZC/placebo after rescue and increase to 15 g QD if not already at maximum. Follow up at Visit 8 for monitoring of local S-K laboratory value.

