## 6.6 Dose Modification

The investigator should rely primarily on local laboratories to make rapid or urgent decisions regarding clinical management. This includes monitoring of electrolytes (eg, S-K), renal function (eg, S-Cr), and other parameters that may be needed for appropriate CKD clinical management as per investigator's discretion.

The S-K and S-Cr samples collected and analysed by local laboratory as per the SoA (Section 1.3) or as part of routine clinical practice can also be used to adjust doses of SZC/placebo and lisinopril/valsartan.

During the run-in and maintenance phases, SZC/placebo can be titrated in the range 5 g QOD to 15 g QD. Lisinopril overall dose range/titration steps for this study are 5, 10, 20, or 40 mg QD; valsartan dose range/titration steps are 40, 80, 160, or 320 mg QD (see Table 8). In case of valsartan shortage, see Appendix E for irbesartan information. Temporary discontinuations of SZC/placebo or lisinopril/valsartan are permitted as part of the dosing regimen.

If at any point in the study lisinopril/valsartan treatment is reduced or temporarily discontinued, the investigator should make every effort to restart and maximise the dose of these agents once the cause of the reduction or discontinuation has resolved.

Instructions for dose modification and monitoring and management of S-K during the study are provided in the subsections below.

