**Table 8** **Lisinopril and Valsartan Dose Titration Steps**

Dose steps (daily dose)	Lisinopril (mg) a	Valsartan (mg) a
STEP 1 – Starting dose	10 (5) b	80
STEP 2	20	160
STEP 3	40	320

a Starting dose and dose range may differ per local labels. For example, in Japan, where starting and/or maximum doses are lower than specified above, the following would apply:

- STEP 1: lisinopril 10 mg; valsartan 40 mg
- STEP 2: lisinopril 20 mg; valsartan 80 mg
- STEP 3: lisinopril 20 mg; valsartan 160 mg

b If lisinopril starting dose is 5 mg (eg, if eGFR  $\geq 10$  to  $\leq 30$  mL/min/1.73m^2, or participant is on diuretics, or per local label), stepwise increase in these cases may require an additional step: 5, 10, 20 and 40 mg. eGFR, estimated glomerular filtration rate.

As per Section 4.1.3, if temporary use of irbesartan is necessary due to local market shortage, see [Appendix E](#) for further details, including conversion information for changing from valsartan or other ARBs to irbesartan, ARB dose equivalence ranges, dose modification strategy for irbesartan, and other prescribing information about irbesartan.

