## Appendix B RAASi Therapy Considerations for Inclusion into the Study and Dosing of Lisinopril and Valsartan

### B 1 Guide for Change of Other RAASi therapy into an Equivalent Dose Range for Lisinopril or Valsartan

Other ACEi or ARB SoC dose a	Lisinopril (mg) b	Valsartan (mg) b
None or starting daily dose	10 (5) c	80
Mid-range daily dose (doses between starting and maximum dose if applicable)	20 (10) c	160
Maximum daily dose	20 (20) c	160

a See Appendix B 2 for starting, mid-range (if applicable), and maximum daily dose of each individual ACEi/ARB drug.

b Starting dose may differ per local labels. For example, in Japan, where starting doses are lower than specified above, the following would apply:

- Starting: lisinopril 10 mg; valsartan 40 mg
- Mid-range: lisinopril 20 mg; valsartan 80 mg
- Maximum: lisinopril 20 mg; valsartan 160 mg

c If eGFR  $\geq$  10 to  $\leq$  30 mL/min/1.73m^2 or participant is on diuretics, or per local label, lisinopril starting, mid-range, and maximum are 5, 10, and 20 mg, respectively.

ACEi, angiotensin converting enzyme inhibitor; ARB, angiotensin II receptor blocker; eGFR, estimated glomerular filtration rate; SoC, standard of care.

For subsequent up-titration of lisinopril or valsartan during the run-in phase, see Sections 6.6.2 and 6.6.3.

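### Section 6.6.4 acts on the RAASi dose step, but Table 8 gives no single step to lisinopril 10 mg after a 5 mg start, or to lisinopril 20 mg in Japan

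*Protocol*

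**What the plan says.** Section 6.6.4 covers the period from randomised withdrawal to Week 6 and names Table 8 as the ladder for stepwise adjustments. At Visit 7, two days after randomisation, the rules are:

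- **S-K > 5.5 mmol/L, bottom of the ladder:** "Lisinopril/valsartan is at the lowest dose, permanently discontinue lisinopril/valsartan and consider short-term rescue therapy and management of hyperkalaemia as per SoC".
- **S-K > 5.5 mmol/L, higher on the ladder:** "Lisinopril/valsartan is at mid-range (STEP 2) or maximum dose (STEP 3), pause lisinopril/valsartan and SZC/placebo, and give short-term rescue therapy".
- **S-K > 5.0 to 5.5 mmol/L:** reduce lisinopril/valsartan one step. With SZC/placebo already at 15 g, the exception is "If lisinopril/valsartan is at the lowest dose (STEP 1), pause dosing and assess re-initiation of these agents at STEP 1 starting doses".

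Visit 8 applies the same structure to participants who were not rescued at Visit 7.

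The main rows of Table 8 have three steps: lisinopril 10 (5), 20 and 40 mg, and valsartan 80, 160 and 320 mg. Footnote b covers participants started on lisinopril 5 mg, for example with eGFR 10 to 30 or on diuretics: "stepwise increase in these cases may require an additional step: 5, 10, 20 and 40 mg". It assigns no step numbers. Footnote a gives a Japan ladder in which STEP 2 is lisinopril 20 mg and the next line is "STEP 3: lisinopril 20 mg; valsartan 160 mg".

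**The concern.** The algorithm works only if each dose maps to exactly one step, because the step separates permanent loss of RAASi from a pause, and a pause from a reduction. Table 8 fails that test in two places, and both can be reached in this trial. Eligibility starts at eGFR 25, and stable thiazide or loop diuretics are allowed, so 5 mg starters are expected. Japan is on the SAP's country list (Appendix 7.2).

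The rules apply 2 and 7 days after SZC withdrawal, when the protocol itself expects hyperkalaemia in placebo participants (Table 3). Keeping participants on RAASi is a central part of the trial's rationale. Time to first lisinopril/valsartan dose decrease is the second endpoint in the secondary testing sequence. Who stays on RAASi should not depend on how a site reads a footnote.

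**Working it through.** No sample size, power or event figure is involved. The check applies the Visit 7 rules to each printed dose, under each reading of the ladder, in the two potassium bands.

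**1. Lisinopril 10 mg in a participant started on 5 mg**

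| How 10 mg is read | Basis | S-K > 5.0 to 5.5 | S-K > 5.5 |
|---|---|---|---|
| STEP 1 | Table 8 main row, which prints 10 (5) | Pause | Permanent discontinuation |
| Second rung, taken as STEP 2 or mid-range | Order in footnote b | Reduce to 5 mg | Pause and rescue |
| Extra rung with no number (5 = STEP 1, 20 = STEP 2, 40 = STEP 3) | Footnote b read literally | Reduce to 5 mg | No branch: neither lowest nor STEP 2 or 3 |

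The four-rung ladder is in real use. Section 6.6.3 expects up to three up-titration steps of two weeks each (3 × 2 = 6 weeks) to reach the maximum. From 5 mg, 5→10→20→40 is three increases. From STEP 1 of the main rows, 10→20→40 is two.

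**2. Lisinopril 20 mg on the Japan ladder (10, 20, 20)**

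- S-K > 5.0 to 5.5, dose regarded as STEP 3: one step down is 20→20 mg, a change of 20 − 20 = 0 mg.
- S-K > 5.0 to 5.5, dose regarded as STEP 2: one step down is 20→10 mg.
- S-K > 5.5: pause and rescue on either label, so there is no conflict.

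Section 8.1.2 counts the first change to a dose below that taken at randomisation. For a participant randomised on 20 mg, 20→10 is an event and 20→20 is not.

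**3. Doses where the Table 8 readings agree**

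Lisinopril 40 mg gives reduce to 20, or pause. Lisinopril 20 mg outside Japan gives reduce to 10, or pause, whether it is STEP 2 or the third rung of footnote b. Valsartan 160 and 320 mg each give one action per band.

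**4. Supporting inconsistencies**

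- Section 6.6 says "valsartan dose range/titration steps are 40, 80, 160, or 320 mg QD" and cites Table 8, whose main rows start at 80 mg; 40 mg appears there only in the Japan footnote.
- For S-K > 5.5, the Visit 7 branch names the lowest dose with no step label, while the matching Visit 8 branch labels it STEP 1.
- Appendix B 1, footnote c, covers the same kind of participant as Table 8 footnote b but states "lisinopril starting, mid-range, and maximum are 5, 10, and 20 mg, respectively". Footnote b runs to 40 mg.

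**The case against.** The strongest reply is that Section 6.6.4 already resolves most of this. It names Table 8, and several of its branches equate the lowest dose with STEP 1. A careful reader of 10 (5) with its footnote would take 5 mg as STEP 1 for a 5 mg starter, which weakens the permanent-discontinuation reading of 10 mg. That is fair, but the extra rung still has no step number, so 10 mg at S-K > 5.5 remains either mid-range by inference or outside every branch. The Japan duplication is not resolved by any cross-reference.

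Three further points for the other side stand:

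- **Valsartan 80 mg.** A reader might infer the same gap here, because Section 6.6 lists a rung below it. Under the governing table 80 mg is STEP 1, and the Section 6.6 list reads naturally as the study-wide range, with 40 mg a local-label dose. This is a loose cross-reference.
- **Appendix B 1.** A reader might infer that the protocol sets two maximum lisinopril doses. B 1 is a guide for switching from other agents at run-in entry, Section 6.6.4 does not cite it, and it sends up-titration to Sections 6.6.2 and 6.6.3. Its labels are worth aligning but do not govern Visit 7.
- **Existing safeguards.** At S-K > 5.0 to 5.5, SZC/placebo is raised to 15 g if not already there, potassium is rechecked in 5 (±1) days, and Section 6.6.5 allows down-titration on investigator judgment. The paths after S-K > 5.5 also partly converge: at Visit 8, S-K > 5.0 after rescue at Visit 7, or rescue continued in the past 72 hours, leads to permanent discontinuation.

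**Conclusion.** The rule is defective as written, in a limited way. Followed literally, it gives no definite action for lisinopril 10 mg after a 5 mg start. It also gives an empty reduction for Japanese participants regarded as being at STEP 3 of lisinopril. Both faults lie inside the table that Section 6.6.4 names as governing.

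Four stronger conclusions are tempting but not supported:

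- One participant at one potassium value could face permanent discontinuation, a pause or an unchanged dose. No printed dose and band gives all three. Permanent discontinuation arises only at S-K > 5.5, and a nominal reduction with no change arises on Table 8 only at > 5.0 to 5.5.
- Reading discontinuation for pause would distort the dose-decrease endpoint. If dose 0 counts as a decrease, as the SAP's exposure section (4.1.9.2) suggests without saying so for this endpoint, both give an event on the same date. Only the Japan duplication clearly changes whether an event is recorded.
- The arms would be biased against each other. Sites are blinded and randomisation is stratified by country, so what is shown is added variation in RAASi exposure.
- Many participants are affected. The documents give no shares by starting dose, diuretic use or country, and the run-in aims for maximum doses, which should reduce the number on low rungs.

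The Appendix C algorithm diagram is not legible in the text reviewed, so whether it repeats or resolves the ambiguity was not checked.

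**What to change.** Reconcile Table 8 (with footnotes a and b), Section 6.6 and the lowest-dose wording in Section 6.6.4. Each dose should have exactly one step for each drug and label region, and the lowest step should be named. Use the same wording at Visits 7 and 8, align the Appendix B 1 labels, and check Appendix C against the result. The clinical team decides which ladder and which action apply; no dose or rule is proposed here.

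The cost is a wording amendment and a site memo, with no new procedure or data. The SAP's amendment history records premature termination. If dosing has stopped, the change matters for any reuse of the algorithm. In that case the study report could state how steps were interpreted for 5 mg lisinopril starters and for Japan when the dose-decrease results are presented.

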##### **Visit 8 (5 [ $\pm 1$ ] days after Visit 7)**

- If S-K is  $\geq 3.5$  and  $\leq 5.0$  mmol/L and lisinopril/valsartan treatment has continued at any dose since Visit 7, the dose will remain unchanged, and the participant will follow the SoA (Section 1.3) to return for Visit 9.

- If S-K is  $\geq 3.5$  and  $\leq 5.0$  mmol/L and lisinopril/valsartan treatment was paused on Visit 7, but no rescue was given, re-initiate these agents at starting doses (STEP 1). Follow up 5 ( $\pm 1$ ) days later in an unscheduled visit for a local S-K laboratory measurement.
- If S-K is  $\geq 3.5$  and  $\leq 5.0$  mmol/L WITH rescue given at Visit 7 (but not during past 72 hours), consider re-initiating lisinopril/valsartan at starting dose (STEP 1). If rescue was continued during past 72 hours, permanently discontinue lisinopril/valsartan and return to SoC as per local practice. Follow up 5 ( $\pm 1$ ) days later in an unscheduled visit for a local S-K laboratory measurement.
- If S-K is  $> 5.0$  WITH rescue given at Visit 7, permanently discontinue lisinopril/valsartan and return to SoC as per local practice.
- If S-K is  $> 5.0$  and  $\leq 5.5$  mmol/L and no rescue was given at Visit 7 and SZC/placebo IS NOT at maximum of 15 g QD, increase SZC/placebo to 15 g QD AND reduce lisinopril/valsartan one step. If lisinopril/valsartan is at the lowest dose (STEP 1), pause dosing and assess re-initiation of these agents at starting doses during the next visit. The participant must return 5 ( $\pm 1$ ) days later to an unscheduled visit for a local S-K laboratory measurement.
- If S-K is  $> 5.0$  and  $\leq 5.5$  mmol/L and no rescue was given at Visit 7 and SZC/placebo IS already at 15 g QD, reduce lisinopril/valsartan one step. If lisinopril/valsartan is at the lowest dose (STEP 1), pause dosing and assess re-initiation of these agents at STEP 1 starting doses during the next visit. The participant must return 5 ( $\pm 1$ ) days later to an unscheduled visit for a local S-K laboratory measurement.
- If S-K is  $> 5.5$  mmol/L and no rescue was given at Visit 7 and:
  - Lisinopril/valsartan is at the lowest dose (STEP 1), permanently discontinue lisinopril/valsartan and consider short-term rescue therapy and management of hyperkalaemia as per SoC at the investigator's discretion and local practice. Follow up 5 ( $\pm 1$ ) days later to an unscheduled visit for a local S-K laboratory measurement.
  - Lisinopril/valsartan is at mid-range (STEP 2) or maximum dose (STEP 3), pause lisinopril/valsartan and SZC/placebo, consider short-term rescue therapy as per SoC at the investigator's discretion; re-start SZC/placebo after rescue and increase to 15 g QD if not already at maximum. Follow up 5 ( $\pm 1$ ) days later to an unscheduled visit for a local S-K laboratory measurement.

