### **6.5.2      Rescue Medication**

Rescue therapy for controlling hyperkalaemia is defined as any short-term (24 to 48 hours) therapeutic intervention during the run-in and maintenance phases, that is considered necessary as per the investigator's judgment and in accordance with local practice patterns to reduce S-K in the setting of an AE of severe hyperkalaemia. Rescue therapy is recommended

in general if S-K > 6.0 mmol/L unless otherwise specified in the protocol (see Section 6.6.4). Rescue therapy may include, but is not limited to, insulin/glucose, beta adrenergic agonists, sodium bicarbonate as well as dialysis, or other forms of renal replacement treatments, and other potassium binders including SPS, CPS, patiromer sorbitex calcium (Veltassa®) given for short-term control of severe hyperkalaemia. SZC/placebo must be temporarily discontinued while rescue therapy is administered.

All potassium binders other than SZC are considered restricted medications and can be used only for short-term rescue. They must not be used for chronic treatment during the study. Any participant who receives chronic treatment with potassium binders other than SZC/placebo must be discontinued from SZC/placebo study intervention.

Rescue medication for hyperkalaemia will not be provided as part of study medications.

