#### Visit 4 (Day 13 $\pm$ 3 days)

- If S-K is  $\geq 3.5$  and  $< 4.7$  mmol/L, and if not already on maximum dose, increase lisinopril/valsartan one step; follow 2 weeks later with a local laboratory measurement of S-K.
- If S-K is  $\geq 4.7$  and  $\leq 5.5$  mmol/L, increase SZC to 15 g QD, repeat S-K in 48 hours and follow instructions in [Appendix C](#); if lisinopril/valsartan is increased one step based on these instructions, follow 2 weeks later with a local laboratory S-K measurement.

- If S-K is  $> 5.5$  and  $\leq 6.0$  mmol/L, temporarily discontinue lisinopril/valsartan, increase SZC to 15 g QD, repeat S-K in 48 hours and follow instructions in [Appendix C](#). After 48 hours:
  - If S-K is  $\geq 3.5$  and  $< 4.7$  mmol/L, restart lisinopril/valsartan at previous dose.
  - If S-K is  $\geq 4.7$  and  $\leq 5.0$  mmol/L, restart lisinopril/valsartan at lower dose if available. If lower dose is not available, consider reinitiating lisinopril/valsartan at starting dose 2 weeks after visit or permanently discontinue lisinopril/valsartan as per investigator judgment.
  - If S-K is  $> 5.0$  and  $\leq 6.0$  mmol/L, reduce or permanently discontinue lisinopril/valsartan per investigator judgment.
  - If S-K is  $> 6.0$  mmol/L, permanently discontinue lisinopril/valsartan, continue short-term rescue therapy as per SoC.
- If S-K  $> 6.0$ , temporarily discontinue lisinopril/valsartan, increase SZC to 15 g QD, repeat S-K in 48 hours, consider short-term rescue therapy as per SoC. Per [Appendix C](#), after 48 hours:
  - If S-K is  $\geq 3.5$  and  $< 4.7$  mmol/L, restart lisinopril/valsartan at previous dose.
  - If S-K is  $\geq 4.7$  and  $\leq 5.0$  mmol/L, restart lisinopril/valsartan at lower dose if available. If lower dose is not available, consider reinitiating lisinopril/valsartan at starting dose 2 weeks after visit or permanently discontinue lisinopril/valsartan as per investigator judgment.
  - If S-K is  $> 5.0$  and  $\leq 6.0$  mmol/L, reduce or permanently discontinue lisinopril/valsartan per investigator judgment.
  - If S-K is  $> 6.0$  mmol/L, permanently discontinue lisinopril/valsartan, continue short-term rescue as per SoC.
- Follow 2 weeks after any dose adjustment with a local laboratory S-K measurement or earlier if clinically indicated.

Unscheduled visit for monitoring of lisinopril/valsartan up-titration 2 weeks after Visit 4 (or earlier if clinically indicated)

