### Unscheduled Visit (5 [ $\pm 1$ ] days after Visit 8)

- If S-K is  $\geq 3.5$  and  $\leq 5.0$  mmol/L and lisinopril/valsartan was paused at Visit 8, restart lisinopril/valsartan at starting dose and schedule follow-up visits as per KDIGO 2020 Clinical Practice Guideline for Diabetes Management in CKD ([KDIGO 2020](#), Practice Point 1.2.2); the participant will in addition follow the SoA (Section 1.3) and return for Visit 9.
- If S-K is  $> 5.0$  mmol/L, permanently discontinue lisinopril/valsartan if on treatment, and consider short-term rescue therapy and management of hyperkalaemia as per SoC at the investigator's discretion and local practice.

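### At Visit 8, the S-K > 5.5 mmol/L branch for STEP 2 or 3 pauses SZC/placebo unconditionally but states a restart only for participants who are rescued

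*Protocol*

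**What the plan says.** **The branch in question.** Protocol Section 6.6.4, Visit 8, for S-K > 5.5 mmol/L with no rescue at Visit 7, splits by lisinopril/valsartan dose step. At STEP 2 or 3 the site is told: "pause lisinopril/valsartan and SZC/placebo, consider short-term rescue therapy as per SoC at the investigator's discretion; re-start SZC/placebo after rescue". On restart the dose goes to 15 g QD if it is not already there. A local S-K check follows 5 (±1) days later.

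**The STEP 1 branch at the same S-K.** "Lisinopril/valsartan is at the lowest dose (STEP 1), permanently discontinue lisinopril/valsartan and consider short-term rescue therapy". It contains no instruction to pause SZC/placebo.

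**The unscheduled visit after Visit 8.** There are two bullets. For S-K 3.5 to 5.0 mmol/L, if "lisinopril/valsartan was paused at Visit 8, restart lisinopril/valsartan at starting dose". For S-K > 5.0 mmol/L, lisinopril/valsartan is permanently stopped if the participant is taking it, and rescue is considered. Neither bullet mentions SZC/placebo.

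**The general rules.** Section 6.5.2: "SZC/placebo must be temporarily discontinued while rescue therapy is administered". Appendix C footnote c says the same and allows resumption once rescue is complete. Section 7.1.2 lists hypokalaemia as the additional hold reason for SZC/placebo, and lists hyperkalaemia under lisinopril/valsartan. It also lets a held participant resume once the investigator judges the condition stable.

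**The concern.** Three parts of the Visit 8 bullet do not fit together: the pause is unconditional, rescue is discretionary, and the restart is written only for those rescued. A site that considers rescue and decides against it has followed the protocol, yet Section 6.6.4 does not tell it what to do next with SZC/placebo.

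The instruction is blinded and identical in both arms, but its effect is not. Pausing placebo removes nothing, whereas pausing SZC removes the potassium binder from a participant whose S-K is above 5.5 mmol/L. The recheck S-K, which decides what happens to lisinopril/valsartan, is then taken off the binder. The main issue is therefore the handling of hyperkalaemic participants. A secondary issue is avoidable off-drug time in the SZC arm, which the treatment-policy strategy in SAP Section 4.2 keeps in the main analyses.

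**Working it through.** The documents give no figure to reproduce. The check sets the instructions side by side and then works out the timing.

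**1. What happens to SZC/placebo**

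| Place in the protocol | Situation | SZC/placebo instruction |
|---|---|---|
| 6.6.4, Visit 8 | S-K > 5.0 to 5.5, no rescue at Visit 7 | Raise to 15 g QD if below it |
| 6.6.4, Visit 8 | S-K > 5.5, no rescue at Visit 7, STEP 1 | None |
| 6.6.4, Visit 8 | S-K > 5.5, no rescue at Visit 7, STEP 2–3 | Pause; restart after rescue |
| 6.6.4, Visit 8 | S-K > 5.0, rescue given at Visit 7 | None |
| 6.6.4, unscheduled visit | Either S-K band | None |
| 6.5.2; Appendix C footnote c | Rescue being administered | Hold during rescue |
| 7.1.2 | Specific hold reason for SZC/placebo | Hypokalaemia |

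Only the STEP 2–3 row holds SZC/placebo for hyperkalaemia without making the hold depend on rescue.

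**2. The two paths through the STEP 2–3 branch**

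- Rescue given: pause, rescue, restart at 15 g QD. The path is complete and agrees with Section 6.5.2.
- Rescue not given: pause, then no restart step at Visit 8 and none at the unscheduled visit. If S-K has returned to 3.5–5.0 mmol/L, the text restarts lisinopril/valsartan without saying whether SZC/placebo is back on.

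**3. Is non-rescue foreseeable?** Section 6.5.2 generally recommends rescue above 6.0 mmol/L but defers to Section 6.6.4 where that section says otherwise. In this branch Section 6.6.4 asks only that rescue be considered, so withholding it is compliant.

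**4. Timing**

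- Visit 8 is nominally Day 8 of the maintenance phase (Table 2).
- The recheck is 5 (±1) days later: 5 − 1 = 4 to 5 + 1 = 6 days, nominally Day 12 to Day 14.
- Section 6.6.1 and Appendix C also call for S-K re-sampling after 2 weeks, or earlier, when lisinopril/valsartan is decreased or discontinued for hyperkalaemia: 8 + 14 = Day 22 at the latest.
- For scale, the maintenance phase is 104 × 7 = 728 days, and 6 / 728 = 0.8%. For one participant, the nominal gap itself is a very small share of follow-up.

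**The case against.** **The pause may simply be the rescue hold.** The bullet can be read as one sequence of pause, rescue and restart, in line with Section 6.5.2 and footnote c. That reading is plausible and may be what was intended. But the bullet makes rescue optional and does not make the pause conditional on it, so the reading has to be supplied by the site.

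**Section 7.1.2 fills the gap.** In part it does: the investigator may resume SZC/placebo once the condition is judged stable. The interruption is therefore unspecified, and resumption is not barred. Section 7.1.2 does not say how that judgement applies to a participant held because S-K is still high.

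**Stronger readings that the documents do not support:**

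- *About 35 days off drug.* A reader might run from Visit 8 to Visit 9 (Day 43 − Day 8 = 35). This ignores the recheck at 4 to 6 days, the re-sampling at about 2 weeks under Section 6.6.1 and Appendix C, and Section 7.1.2. The Appendix C flow chart is also not visible in the text available, so it cannot be said to lack a restart path.
- *Dilution of time to first lisinopril/valsartan dose decrease.* Protocol Section 8.1.2 counts the first change to a dose below that at randomisation. In this branch the drug is itself paused at Visit 8, and SAP Section 4.1.9.2 tabulates an interruption as dose 0. Even if a pause were not counted, the restart in the unscheduled-visit bullet is at the starting dose, below STEP 2 or 3. The decrease does not wait on SZC/placebo.
- *An S-K > 5.0 mmol/L at the recheck forces permanent discontinuation of lisinopril/valsartan.* That bullet applies to participants on treatment. Whether it reaches someone already paused is unclear.
- *A contradiction with run-in.* At Visit 4, Section 6.6.3 says "temporarily discontinue lisinopril/valsartan, increase SZC to 15 g QD" for S-K > 5.5 mmol/L. But run-in SZC is open-label, and Section 6.6.4 explains that its own instructions are specific because treatment is blinded. This is a difference between phases.
- *The same fault at Visit 7.* Visit 7 tells the site to give rescue for 24 to 48 hours, although it adds the investigator's discretion. Its wording needs a consistency check, but it is not the same gap.

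**Conclusion.** The point holds for one branch: Visit 8, S-K > 5.5 mmol/L, no rescue at Visit 7, lisinopril/valsartan at STEP 2 or 3, and rescue considered but not given. There the protocol pauses SZC/placebo and Section 6.6.4 states no restart. That conflicts with the rescue-linked hold in Section 6.5.2 and Appendix C footnote c, and it does not match the hold reasons in Section 7.1.2 or the STEP 1 branch.

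Read literally, an SZC-arm participant on this path is off the binder while hyperkalaemic for a nominal 4 to 6 days, or less if the investigator resumes under Section 7.1.2. This assumes that sites follow the bullet as written and that the unseen Appendix C flow chart does not override it.

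The number of participants affected is not given. Some attenuation of the slope contrast is possible in principle, but it cannot be quantified and may be small. The reason to correct the text is that a compliant site can take a hyperkalaemic participant off the study drug with no stated next step.

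**What to change.** Reconcile the Visit 8 bullets and the following unscheduled visit in Section 6.6.4 with Sections 6.5.2 and 7.1.2 and Appendix C footnote c. The protocol should state:

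- what happens to SZC/placebo in this branch when rescue is not given;
- when it restarts, including what the unscheduled visit should do about it;
- whether STEP 1 and STEP 2–3 are meant to differ at the same S-K.

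Also check that the Visit 7 wording, which both directs rescue and leaves it to discretion, agrees with the result. The clinical team decides the rule; none is proposed here.

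The cost is a few sentences, with no added visits or data. The SAP amendment history records that the study was terminated early, so for this trial the sponsor could instead clarify the intended reading and report how many participants in each arm took this branch without rescue. The protocol already requires recording of the S-K values that trigger dose changes (Section 6.6.1), the times and reasons for temporary discontinuation (Section 7.1.2), and whether an adverse event required rescue (Section 8.3.2).
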